Secondary outcomes will be assessed in a similar way by establishing diagnostic plots to identify the most appropriate regression approach; logistic for dichotomous outcomes, ordinal for ordered categorical outcomes, linear for continuous outcomes and fractional for proportions. Stratification factors and baseline covariates will be included within the model.

If the missing data exceeds 5%, sensitivity analyses will be performed using a pattern mixture approach and multiple imputation to compare the sensitivity of conclusions to varying assumptions about the missing data, particularly whether data is missing at random (MAR) or missing not at random (MNAR). This allows for an assessment of both random and systemic bias. Results based on complete data analysis, MAR and MNAR will be presented to explore the influence of missing data on outcomes observed.

We will conduct a Complier Average Causal Effects (CACE) analysis using an instrumental variable framework to explore the impact of compliance on the primary outcomes at different levels of compliance, both fidelity to the steps involved in each tier and quintiles of compliance. CACE weights the analysis by the ITT treatment effect by the proportion of compliance, this allows the estimation of unbiased treatment effects and maintains the allocation in the analysis.

Objective 3: For staff we will explore the differences between the groups in terms of overall wellbeing, perceptions of working in a trauma informed manner and confidence in working with young people who have experienced adverse childhood experiences derived from the SWEMWBS and ARTIC questionnaire at months 6 and 12 using linear regression adjusted for baseline score and service. Staff turnover and proportion absence will be assessed in a similar manner using fractional regression.

Objective 5: Stepwise regression analysis will be performed to model the relationship between pre-randomisation factors and demographics, on observed outcomes at 6 months.

Interaction terms with allocation arm will be included in the analysis, and a significance level of 0.1 will be used to determine which factors are to be included in the regression model. Pre-randomisation factors will include sex, age, ethnicity, IMD, family cohesion, adverse childhood experiences assessed by the service, and process measures, staff perceptions, staff confidence, and therapeutic alliance. The allocated arm will be included in this analysis as an interaction term.

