Secondary outcome and data source	
Young Person:
 
Number of delinquent offences in the past 12 months derived from the SRDS at months 6 and 12.
 
Self-report behaviour and personality attributes (overall emotional and behavioural difficulties, emotional symptoms, conduct problems, hyperactivity, peer relationships, prosocial behaviour, externalising behaviours, internalising behaviours) derived from the Strengths and Difficulties Questionnaire (SDQ) at month 6 and 12.
 
Self-report non-psychotic mental health derived from the General Health Questionnaire (GHQ12) at months 6 and 12.
 
Self-report wellbeing derived from the Short Warwick Edinburgh Mental Wellbeing Scale (SWEMWBS) at month 6 and 12.
 
Self-report family cohesion, expressiveness and conflict derived from the Brief Family Relationship Scale (BFRS) at month 6 and 12.
 
Self-report Client Service Receipt Inventory (CSRI) to assess police involvement at month 6 and 12 (arrests, cautions, charges, court attendance), educational outcomes (suspensions, exclusions, managed moves) and employment status.
 
Staff
 
Self-report Attitudes Related to Trauma Informed Care

	
(ARTIC) measured before training, and at month 6 and 12 after training.
 
Self-report Short Warwick Edinburgh Mental Wellbeing Scale (SWEMWBS) before training and at month 6 and 12 after training.
 
Staff turnover throughout the trial and staff absence throughout the study period.

--	--

SAP version history

Version	Date	Changes made and reason for revision
1.0 [original]		

Table of contents

Introduction 5

Intervention 6

Design overview 9

Sample size calculations overview 12

Analysis 13

Introduction

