The primary outcome relates to the participant and is the quantity of self-reported delinquent acts in the six months after randomisation assessed using the SRDS. The quantity of delinquent acts is calculated as the sum of positive endorsements for each of the nineteen questions in the SRDS. Two datasets will be created for statistical analysis, the primary analysis will be based on the intention to treat (ITT) dataset. The secondary analyses will examine intervention effects under different scenarios for compliance with allocation (see compliance section below): complier average causal effects (CACE); and per protocol (PP).

The ITT dataset contains all available data for participants who were randomised, regardless of whether they complied with allocation. This dataset will include participants who were withdrawn/withdrew from the trial post-randomisation. These analyses are a lower bound estimate of intervention effects as they represent the effect of offering an intervention, rather than the effect of receiving the intervention.

The primary outcome is the quantity of offences at 6-months post-randomisation. We expect the primary outcome will take the form of a linear distribution. Prior to analysis we will conduct a series of diagnostic tests and assess the underlying assumptions prior to choosing an appropriate and statistically rigorous regression approach. The analysis will take the form of an analysis of covariance using a linear regression. Models will be adjusted by baseline values, quantity of offences in the six months prior to randomisation and stratification factors, service, age group and sex, as covariates. The regression model specification is as follows (eq.1):

$$SRDS6_{i,j} = \alpha + \beta_1(allocation)_{i,j} + \beta_2(SRDS0)_{i,j} + \beta_3(sex)_{i,j} + \beta_4(age)_{i,j} + \beta_5(service)_j + \varepsilon_i$$

Where for participant i within service j ; $SRDS6$ is the 6-month SRDS score, $allocation$ is the allocated group, $SRDS0$ is the baseline SRDS score, sex is the participant sex, age the age group, $service$ the service level dummy variables to adjust for fixed effects and ε_i the individual level error.

An estimate of difference will be generated as a mean difference between the groups and the associated 95% confidence interval.

Secondary outcome analysis

For participants the quantity of offences reported at 12-months will be analysed using similar methods as 6-months (eq. 2).

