$$SRDS12_{i,j} = \alpha + \beta_1(\text{allocation})_{i,j} + \beta_2(SRDS0)_{i,j} + \beta_3(\text{sex})_{i,j} + \beta_4(\text{age})_{i,j} + \beta_5(\text{service})_j + \varepsilon_i$$

Where for participant i within service j ; $SRDS12$ is the 12-month SRDS score, $allocation$ is the allocated group, $SRDS0$ is the baseline SRDS score, sex is the participant sex, age the age group, $service$ the service level dummy variables to adjust for fixed effects and ε_i the individual level error.

Other secondary outcome analysis at months 6 and 12, will be based on the ITT dataset. All secondary outcomes are continuous in nature, and after the examination of diagnostic plots to establish that the underlying assumptions for a linear analysis of covariance are met, they will be using an approach similar to that used in the primary outcome analysis (eq.3).

$$OUT_{i,j} = \alpha + \beta_1(\text{allocation})_{i,j} + \beta_2(OUT0)_{i,j} + \beta_3(\text{sex})_{i,j} + \beta_4(\text{age})_{i,j} + \beta_5(\text{service})_j + \varepsilon_i$$

Where for participant i within service j ; OUT is the 6 or 12-month outcome, $allocation$ is the allocated group, $OUT0$ is the baseline outcome value, sex is the participant sex, age the age group, $service$ the service level dummy variables to adjust for fixed effects and ε_i the individual level error.

Staff outcomes (ARTIC score, wellbeing and rates of absence) will be analysed using an analysis of covariance adjusted for baseline values and stratification factors: service and specialist versus generic.

Outcomes will be presented for each allocated group as means and the associated estimates of precision, 95% confidence intervals.

Subgroup analyses

To maintain power in the analysis we will avoid analysing sub-groups and instead use the whole sample for latent class analysis to explore for the emergence of clusters of participants who may have a differential response to the RBT intervention. Latent class approaches allow for clusters to emerge from the data rather than being pre-specified. In addition to the baseline variables being collected we will also include measures of ethnicity, material deprivation and therapeutic alliance assessed at month 6 using the short revised therapeutic alliance scale for children (TASC-r; (Shirk and Saiz, 1992)).

Further analyses

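### The SAP calls every secondary outcome continuous, which is wrong for its own police, education and employment outcomes and departs from the protocol's models by outcome type

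*SAP*

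**What the plan says.** **Secondary outcomes, SAP.** The section on secondary outcome analysis says "All secondary outcomes are continuous in nature". Equation 3 applies "after the examination of diagnostic plots to establish that the underlying assumptions for a linear analysis of covariance are met", and in it "OUT is the 6 or 12-month outcome". No other model is named. Results are to be given for each arm as means with 95% confidence intervals.

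**Outcome list, SAP.** The summary table at the front includes, from the Client Service Receipt Inventory (CSRI), "arrests, cautions, charges, court attendance), educational outcomes (suspensions, exclusions, managed moves) and employment status". It also lists staff turnover and staff absence.

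**Staff outcomes, SAP.** Analysis of covariance is specified for trauma-care attitudes, wellbeing and absence rates. Turnover is not mentioned there.

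**Protocol, Analysis.** For secondary outcomes the model follows the type of variable: "logistic for dichotomous outcomes, ordinal for ordered categorical outcomes, linear for continuous outcomes and fractional for proportions". Under Objective 3, staff turnover and the proportion of absence are assigned to fractional regression.

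**Primary outcome, SAP.** The text says "We expect the primary outcome will take the form of a linear distribution" and places diagnostic checks "prior to choosing an appropriate and statistically rigorous regression approach". It then commits to linear regression and writes out equation 1, with a mean difference as the reported effect.

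**The concern.** A SAP exists to settle the model for each outcome before the data are seen. Here a general rule is false for several outcomes to which it applies. The protocol defers to the SAP for analysis detail, so the SAP's rule would be expected to govern.

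An analyst who follows the text literally would regress employment codes on allocation and report a mean. An analyst who notices the problem would have to pick another model after seeing the outcome data, because none is named. Turnover, a listed outcome, would reach analysis with no plan in the SAP. The CSRI items matter because Objective 2 of the protocol names school, work and criminal justice involvement among the effects to be evaluated.

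**Working it through.** **1. The general rule against the outcome list.** The CSRI entry names four police-contact items, three school items and employment status: 4 + 3 + 1 = 8 outcomes. The documents do not say how each is coded. The possibilities are:

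| Outcome | Plausible coding | Continuous? | Model type in the protocol |
|---|---|---|---|
| Four police items | yes/no or count | No | logistic if yes/no; none named for counts |
| Three school items | yes/no or count | No | logistic if yes/no; none named for counts |
| Employment status | yes/no or several categories | No | logistic, or ordinal if the categories are ordered |
| Staff absence | proportion of days | Bounded 0 to 1 | fractional |
| Staff turnover | left or stayed, or a proportion | No | fractional |

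The rule fails for all eight CSRI items under any of these codings. The protocol also has a gap: it names no count model.

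**2. Can equation 3 be applied to employment status?** Give three unordered categories the codes a, b and c, and let the between-arm differences in category proportions be p, q and r, with p + q + r = 0. The mean difference is a·p + b·q + c·r. If p = 0, then r = −q and the difference is (b − c)·q. Swapping the two labels b and c reverses its sign. The result depends on arbitrary codes, so it estimates nothing.

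**3. Does the diagnostic step rescue it?** No. The condition says what must be true for the linear model to be used, but not what happens otherwise. The only logistic regression in the SAP is for predicting missingness. Medians, frequencies and percentages are provided for, but only in baseline tables (Imbalance at baseline).

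**4. Is the test invalid for counts and yes/no items?** First, the planned size. With d = 0.25, two-sided alpha 0.05 and 80% power, n per arm = 2(1.960 + 0.842)²/0.25² = 251.2, rounded up to 252. The exact t-test gives 252.13, rounded up to 253, so 506 in total. Then 506/0.90 = 562.2, against 562 in the plan. The figure is reproduced as a comparison of two means.

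Next, linear analysis of covariance adjusted for baseline was simulated with 253 per arm, no treatment effect and 4,000 runs. The distributions are assumptions:

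- Skewed count (mean 2, dispersion 2, baseline sharing the same frailty): rejection rate 0.048.
- Binary outcome (0.05 + 0.30 × 0.10 = 0.08 overall): rejection rate 0.045.

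The Monte Carlo standard error is √(0.05 × 0.95/4000) = 0.003, so both are compatible with 0.05.

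**5. Primary outcome.** The protocol says the model will probably be a generalised linear regression. That class includes ordinary linear regression. Both documents report a mean difference with a 95% confidence interval. Equation 1 therefore does not contradict the protocol. What remains is wording: a linear distribution is not a recognised distribution for a whole-number score, and the clause on choosing a model sits badly beside a model already chosen.

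**The case against.** The best defence has four parts.

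- **Equation 3 is conditional, and the CSRI items are not named beside it.** True, but the rule covers all secondary outcomes without exception, the list is in the same document, and no alternative is given.
- **Coding and event frequencies are not stated.** This stands in part. Calling the items rare or mostly zero would be an assumption. The protocol also mentions frequency of school attendance, which might be nearly continuous, but attendance is not one of the eight items in the SAP's list.
- **A linear model still gives a valid randomised comparison of means or proportions.** This stands for counts and yes/no items, as step 4 shows. It does not help a category with more than two levels.
- **Restoring the protocol's sentence would not supply a count model.** Correct. The count model is an addition and should be presented as one.

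A reader might go further and infer that the primary model contradicts the protocol, that the headline effect could switch between a difference and a ratio, or that a count model should replace equation 1. The documents do not support these readings. The mean difference is fixed in both, and equation 1 follows directly after the loose clause.

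Any efficiency gain from a count model depends on how the delinquency scale is scored, and the SAP is not consistent on this. Its sample size section refers to the volume of offences; its primary analysis section sums endorsements over nineteen questions. A simulation of a bounded 0 to 19 score (assumed distribution, 506 participants, 10% to 41% zeros in controls, 1,500 runs per setting) put robust Poisson and negative binomial models between 0.4 points below and 2.2 points above linear analysis of covariance in power. With assumed unbounded over-dispersed counts a log-link model looks better, but its type I error was 6.9% with plain robust errors against 4.8% for the linear model, so part of that advantage is test size.

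**Conclusion.** The point holds for the secondary outcomes. The SAP's general statement is false for eight listed CSRI outcomes and departs without explanation from the protocol's models by type. The SAP also replaces the protocol's model for staff absence and gives none for turnover.

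For a multi-category employment status, equation 3 has no interpretable result. For counts and yes/no items the cost is a less useful effect measure and possibly some loss of efficiency; type I error stayed near 5% in the assumed settings. The textual finding needs no assumption about event rates, only that each item is recorded as yes/no, a count or a category.

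For the primary outcome the fault is confined to loose wording around a model that is already specified. Nothing here threatens the primary conclusion. Severity: should-fix.

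**What to change.** **Secondary outcomes**

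1. Delete the sentence declaring all secondary outcomes continuous.
2. Add a table giving, for each CSRI and staff outcome, its coding, type, model, baseline adjustment and effect measure.
3. Use the protocol's models: logistic for yes/no items, ordinal for ordered categories (multinomial if unordered), and fractional for proportions, including staff absence and turnover. If turnover is recorded per person as left or stayed, say so; logistic regression then serves.
4. Add a log-link count model with robust errors for event counts, and state that it extends the protocol's list.
5. Report on a matching scale, such as odds ratios with risk differences, or rate ratios with marginal mean differences, and give frequencies and percentages by arm.
6. Where analysis of covariance is preferred to the protocol's model, give the reason.

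**Primary outcome**

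Remove the description of the expected distribution and the clause on choosing a model. Keep equation 1 and the mean difference as the fixed primary analysis, preferably with robust errors, and name a count model as a sensitivity analysis.

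**Cost.** SAP wording, one table and routine Stata commands; no change to data collection or sample size. Given the 6.9% found with plain robust errors, the count models merit a small-sample correction. If some items prove sparse, the models may not support all the stratification terms, so a rule for falling back to descriptive reporting should be written in now.

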## Impact evaluation

### Study objectives

1. To conduct a prospective RCT to evaluate the efficacy of the Relationship Building Together (RBT) approach compared with business as usual (BAU) on offending behaviour, measured using the Self Report Delinquency Scale (SRDS), over 6- and 12-months post-randomisation, in a population of young people, aged 10-21 years inclusive, accessing services provided by Bridgend Youth Offending Team, Bridgend Youth Development Services, Bridgend Early Help Hubs, Bridgend Edge of Care Services, and Bridgend Children's Services.
2. To evaluate the efficacy of the RBT versus BAU in terms of emotional regulation, peer, prosocial, conduct, hyperactivity, internalising and externalising behaviours (SDQ), wellbeing (SWEMWBS), psychological health (GHQ12), family cohesion (BFRS), school, work, and criminal justice involvement (CSRI), in a population of young people, aged 10-21 years inclusive, accessing services provided by Bridgend Youth Offending Team, Bridgend Youth Development Services, Bridgend Early Help Hubs, Bridgend Edge of Care Services, and Bridgend Children's Services, at 6- and 12-months post randomisation.
3. To evaluate the impact of RBT versus BAU on staff perception of trauma informed care (ARTIC), staff wellbeing (SWEMWBS), staff turnover and staff absence in the 6 and 12 months after training across Bridgend Youth Offending Team, Bridgend Youth Development Services, Bridgend Early Help Hubs, Bridgend Edge of Care Services, and Bridgend Children's Services.
4. To conduct a micro-costing exercise to provide estimates of the cost of delivering the intervention from the perspective of the intervention delivery organisation.
5. To develop a prognostic model exploring the baseline demographics (age, sex, ethnicity, IMD), psychological (SDQ, GHQ12, ACES), therapeutic alliance (TASC-r) and family factors (BFRS) that may impact observed outcomes and using the results to elaborate mechanisms of change and where appropriate revise the intervention logic model.
6. To conduct a latent class analysis to explore potential interactions between population subgroups, intervention received, and outcomes observed.

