### **Analysis**

The proposed analysis is covered in depth in the associated statistical analysis plan.

Objective 1: Participant flow through the study will be presented as a CONSORT diagram. We will present demographics and outcome variables for each group at each time-point. We will explore the validity of the randomisation procedure by presenting baseline outcomes and estimates of precision by allocated group.

Objective 2: The primary outcome is the mean difference between BAU and RBT in number of offences over the 6 months from baseline, assessed using the SRDS at 6-months. The analysis will be conducted using an analysis by intention to treat (ITT) and will include all available data with participants maintained as members of their allocated group, irrespective of whether they complied with the intervention or not. Data will be assessed for distributional assumptions and will probably take the form of a generalised linear regression model, adjusted for baseline stratification covariates and baseline SRDS score. Both the intervention and control vary by service, with a higher to lower hierarchy of complexity running from youth justice, edge of care, children's services, youth development to early help. What is delivered in both the intervention and control group is tailored to the young person's needs. While we

can describe the variety of different sessions delivered in our results, we cannot completely account for it in the analysis, nor can we adjust for any potential contamination due to multi-agency working. Instead, we take a holistic approach, seeing what is delivered as a whole, rather than the sum of its individual parts. Though as complexity is hierarchical across services, we will adjust the analysis for service. This provides the best estimate of effect of how the intervention is proposed to be implemented across diverse services and as a rigorously designed RCT any potential errors introduced will be equally distributed across both groups and mitigated in the analysis. We will apply a multi-level model allowing for participants to be nested within services as a fixed effect. Results will be presented as a mean difference and associated 95% confidence intervals. A secondary analysis will be conducted using a similar approach at month 12.

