Objective 6: To maintain power in analysis we will avoid the analysis of sub-groups. We will use latent class analysis to explore the existence of subgroups within the sample who may have a differential response to the intervention.

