To explore the proposed mechanism of change we will conduct a prognostic linear regression analysis to model the relationship between pre-randomisation factors; age, gender, ethnicity, IMD, SRDS, SDQ, BFRS, GHQ and observed outcomes at 6- and 12- months respectively on the primary outcome at either 6- or 12-months. Interaction terms with allocation arm will be included in the analysis, and a significance level of 0.1 will be used to determine which factors are to be included in the regression model. This analysis will be augmented by an additional

analysis including participants in the RBT arm only using the same pre-randomisation factors but also including process measures of compliance, therapeutic alliance, and interventionist attitude to trauma informed practice.

Interim analyses and stopping rules

No interim analyses are planned. The trial will only be stopped if evidence emerges of a serious adverse event associated with participation in the trial. As the intervention has already been implemented in practice with youth offending populations there is no evidence at the outset that a serious adverse event is likely to occur.

Longitudinal follow-up analyses

Assessments are conducted at baseline, prior to randomisation and then again at months 6 and 12, with 6-months being considered the primary endpoint. Table 2 provides an overview of what measures are being conducted at each time-point.

Outcome	No of items	Baseline	Six months	Twelve months
Primary				
Self-reported delinquency (SRDS) ¹	36	✓	✓	✓
Secondary				
Strength and Difficulties (SDQ) ¹	25	✓	✓	✓
Wellbeing (SWEBWMS)	7	✓	✓	✓
Psychological Distress (GHQ12)	12	✓	✓	✓
Family environment (BFRQ)	16	✓	✓	✓
Receipt Inventory (CSRI)	8	✓	✓	✓
Staff attitudes to trauma informed care (ARTIC)	35	✓	✓	✓
Staff wellbeing (SWEBWMS)	7	✓	✓	✓
Staff turnover & absence	2	✓	✓	✓
Exploratory				
Adverse childhood experiences (ACE-Q)	10	✓		
Process				
Therapeutic relationship	12		✓	
Proportion of sessions planned & delivered	1		✓	✓

Imbalance at baseline

Rather than just assume the randomisation has worked, we will assess observed balance by comparing the means and distributions of the groups created by randomisation for both participants and staff. If they are systematically different across those variables we observe – e.g. always larger / smaller in one group - then that would suggest the randomisation has not been successfully implemented. Baseline equivalence following randomisation will be

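### The latent class analysis for objective 6 stops at the classes: no class-by-allocation estimate is specified, a post-randomisation variable is among the inputs, and there is no power gain over an interaction test

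*SAP*

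**What the plan says.** Objective 6 (Protocol, Study objectives) is to "explore potential interactions between population subgroups, intervention received, and outcomes observed". Two short paragraphs implement it.

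- **Protocol, Analysis, Objective 6:** "To maintain power in analysis we will avoid the analysis of sub-groups". Latent class analysis is to be used to look for subgroups that may respond differently. No further method is given.
- **SAP, Subgroup analyses:** "To maintain power in the analysis we will avoid analysing sub-groups"; instead the team will "use the whole sample for latent class analysis to explore for the emergence of clusters of participants who may have a differential response". On inputs: "In addition to the baseline variables being collected we will also include measures of ethnicity, material deprivation and therapeutic alliance assessed at month 6". On the form of the classes: "Latent class approaches allow for clusters to emerge from the data rather than being pre-specified".

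Neither paragraph gives a class model, a rule for the number of classes, a treatment of uncertain membership, or a model relating class and allocation to SRDS. The latent class analysis in the Protocol's process evaluation concerns non-compliance and does not fill this gap.

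Two neighbouring parts of the plan matter here.

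- **SAP, Further analyses:** a prognostic regression is planned in which "Interaction terms with allocation arm will be included in the analysis, and a significance level of 0.1 will be used" to select factors. The factors are age, gender, ethnicity, IMD, SRDS, SDQ, BFRS and GHQ. The Protocol has similar lists under Objective 5 and in the process evaluation, and both include sex and age. None of the three lists includes service.
- **Protocol, Analysis, Objective 2:** "Both the intervention and control vary by service, with a higher to lower hierarchy of complexity". Service enters SAP equations 1 to 3 as a main effect only.

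**The concern.** A differential-response claim is a claim that the RBT effect on SRDS differs between groups. It needs an estimate of that difference, and the plan as written ends one step short of it. A set of classes could then be reported as groups that may respond differently, with nothing in the analysis to support or refute the statement.

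The month-6 alliance score adds a second problem. RBT is designed to change the relationship between worker and young person, so alliance is a plausible consequence of allocation. If it helps to define the classes, the two arms within a class are no longer guaranteed to be comparable by randomisation, and a class-by-allocation estimate added later would inherit the fault.

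The power rationale also needs care. It can be read as saying that latent classes find differential response without the loss of power that subgroup work brings. If that is not so, the plan puts aside a direct contrast by service, the factor the Protocol itself describes as altering what both arms receive, for a gain that does not exist.

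**Working it through.** **1. The plan's own figure.** Inputs from the SAP, Sample size calculations overview: 0.25 SD, two-sided alpha 0.05, power 80%, 253 per arm. The t-based solution is 252.13 per arm, which rounds up to 253 and a total of 506. Power at 253 per arm is 0.803. The figure reproduces, and it applies to the overall comparison only.

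**2. Power for a difference in effect between two groups.** With SD 1, 1:1 allocation and a group share *p*,

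SE = sqrt(4/(N*p*) + 4/(N(1−*p*))).

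For N = 506 and *p* = 0.5 this is 4/sqrt(506) = 0.178. Power is Φ(δ/SE − 1.96):

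- δ = 0.25: Φ(1.406 − 1.96) = 0.29
- δ = 0.50: Φ(2.812 − 1.96) = 0.80

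These values hold for any equal split, whether it is an observed factor or a class with known membership. For δ = 0.25, power is 20% at a 20/80 split and 13% at 10/90. The documents give no class shares, so these are assumptions.

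**3. Loss from misclassification.** If a proportion *a* is classified correctly in two equal classes, the contrast shrinks by 2*a* − 1. At *a* = 0.85 (assumed) the factor is 0.70:

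- δ = 0.25: Φ(0.175/0.178 − 1.96) = 0.16
- δ = 0.50: Φ(0.350/0.178 − 1.96) = 0.50

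For δ = 0.25 across other assumed accuracies, power is 20% at 90%, 13% at 80% and 8% at 70%.

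**4. Analysing one half of the sample alone.** SE = 2/sqrt(253) = 0.126, so power for a 0.25 SD effect is Φ(1.988 − 1.96) = 0.51, against 0.80 in the whole sample.

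**5. Do classes appear when there are none?** Both simulations drew scores from one continuous factor, with no true classes.

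- N = 562, seven correlated and two independent scores, common diagonal variances, one to three classes chosen by BIC, 60 datasets per setting. Two or more classes were chosen in 95% of runs at an inter-score correlation of 0.1, and in 100% at 0.2, 0.3 and 0.5.
- N = 506, six correlated scores, class-specific diagonal variances, one to four classes, 200 trials. Three classes were chosen in 52% and four in 48%. The split was identical for an RBT effect of 0, a uniform 0.25 and a heterogeneous effect, as it must be when the inputs are baseline scores only.

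When an allocation-by-class test was added to the two-class solution in the second simulation, it rejected in 3.5% of trials with no heterogeneity, 15.5% at a 0.25 SD difference and 56% at 0.5 SD. That test separates the cases; the number of classes does not.

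**6. Month-6 alliance as an input.** In the second simulation an alliance score was added and shifted in the RBT arm by 0, 0.5, 1.0 or 1.5 units. The mean absolute difference between arms in class share was 3.4, 3.8, 4.3 and 4.7 percentage points. The first value is chance imbalance, so membership did move with allocation, but slightly. False rejection stayed at 3.5 to 4.0%. In this set-up, however, the part of alliance not shared with the baseline factor had no effect on SRDS, so it does not measure the bias that would arise if it did.

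**7. An allocation-by-service test.** Assume five equal services (506/5 = 101.2 each) and effects evenly spread over a range *r*. The noncentrality is Σe² × 101.2/4, which is 0.99 for *r* = 0.25 and 3.95 for *r* = 0.5. The 4-df test then has about 10% and 32% power. The 95% CI for the effect within one service has half-width 1.96 × 2/sqrt(101.2) = 0.39 SD.

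**The case against.** Much can be said for the plan.

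- **Forming classes without outcome or allocation is legitimate.** A reader might infer that leaving both out is itself the error. It is not: classes built blind to both and then crossed with allocation are a sound route, and the fix below uses it. Only the second step is missing. Objective 6 shows that the team means to relate classes to intervention and outcome, so the SAP is incomplete; it does not say that emergence is the test.
- **Classes need not emerge under every model.** A reader might infer that clusters appear whatever RBT does. The result in step 5 depends on local independence. With a common full covariance, data of the same structure gave two or more classes in 0% of 60 runs at correlations of 0.1, 0.3 and 0.5. The SAP names no class model, and with month-6 alliance as an input RBT may itself influence membership.
- **The power rationale is partly right.** A reader might call it simply false. Avoiding split-sample analyses does avoid a real loss (51% against 80% in step 4). What fails is the narrower idea that latent classes have more power for differential response than an interaction test.
- **Other interactions are already planned.** A reader might infer that contrasts by all the stratification factors are given up. Allocation interactions with age and sex or gender are planned, though they are screened at 0.1. Only service is absent.
- **The Protocol explains its handling of service.** It declares a holistic view of what is delivered and adjusts for service. That is a reasonable choice for the primary estimate, and it does not prevent an exploratory estimate by service.

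**Conclusion.** The point holds as a gap in an exploratory objective that is cheap to close. The SAP specifies no class-by-allocation estimate on SRDS, so objective 6 cannot be answered as written. It also admits a post-randomisation variable into the class definition, which would weaken any within-class comparison; the simulated movement in membership was small and its size in this trial is unknown. Under local independence, classes tend to appear without any true groups, so their appearance should carry no inferential weight.

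Latent classes offer no power advantage for differential response: 29% for a 0.25 SD difference with known equal classes, the same as for any observed equal split, and about 16% at 85% correct classification. These figures assume an outcome standardised to SD 1, no gain from covariates and no clustering by practitioner. Class shares, classification accuracy and the simulated correlation structure are also assumptions.

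The primary analysis is not affected: it keeps its 80% power whether or not subgroups are examined.

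**What to change.** In SAP, Subgroup analyses:

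1. Form the classes from pre-randomisation variables only, dropping month-6 TASC-r. State the class model and the rule for choosing the number of classes.
2. Fit equation 1 with an allocation-by-class term, allowing for uncertain membership (for example with posterior-probability weights). Report the RBT effect by class and the interaction with 95% CIs, labelled exploratory. Base any statement about differential response on that interaction, not on the emergence of classes.
3. Add an exploratory allocation-by-service estimate, with 95% CIs by service. Allocation-by-age and allocation-by-sex need no new model, since they are already planned.
4. Reword the power rationale to say that split-sample analyses are avoided because each would have low power, without implying that latent classes preserve power for differential response.

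The cost is SAP wording and a few models on data already collected. The downside is low power, especially for service (about 10% for a 0.25 SD range under the assumptions in step 7), so the results should be presented as intervals. A non-significant interaction should not be read as evidence of a uniform effect.
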